4.3 Vulnerable Subjects

We are not including children or women who are pregnant because this study is designed for adults and elderly subjects.

4.4 Strategies for Recruitment and Retention

Expected Participant Flow:

Yearly complete evaluations (including baseline and follow-up) will range from 80-84 (Table 2). Initial screening will be performed through the CES-D, MOSSF, ARES-TM, medication list and AD8. The number of total subjects enrolled will be of 270 to meet the goal of 210 eligible subjects. We anticipate that 17% will be referred to seek treatment due to OSA, while 3-5% will not complete the study evaluations or fulfill inclusion criteria due to cognitive impairment. Based on an average of 24 hours of contact time for each subject (6 h for visits 1-2, 18 h for night 1-2) we will be able to complete 2 subjects per week. To maximize cohort retention we will adopt strategies developed for our own studies²⁰⁹⁻²¹¹ and more than 20 years of experience working with underrepresented groups at the NYU ADC. These will include: *i*) a multicultural staff; *ii*) providing flexible visit options; *iii*) using monetary incentives after completion of all study visits (each subject will receive \$500 after a completed milestone and payment is not contingent upon completing all visits); *iv*) making reminder phone calls prior to scheduled visits; *v*) providing a clinical report to share with their primary care physician; *vi*) sending Annual Holiday letters; *vii*) performing telephone follow-ups after completion of the baseline visit; and, *viii*) participating in local memory walks in Brooklyn together with the *Alzheimer's Association*, and co-sponsoring together with the NYU ADC three annual scientific updates at NYU's Langone Medical Center in both English and Spanish. Previous annual attrition rates at the ADC have been 4% for healthy controls, 13% for MCI and 20% for AD patients. We anticipate that the efforts described above will lead to even higher retention rates (expected 95% at the 2.5 year follow-up)

4.5 Duration of Study Participation

The study will be over the course of 30 months per participant, although we will provide flexible visit options and up to 35 months will be allowed.

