Brief Summary	African-Americans (AAs) have an increased prevalence of both Alzheimer's disease (AD) and vascular risk factors for AD such as diabetes and hypertension when compared to whites. However, in a recent community based study of non-demented elderly, black race was associated with higher amyloid burden after adjusting for vascular risk factors, suggesting the presence of additional physiological differences on AD-risk by race in the early stages of the disease. The purpose of this study is to test whether poor slow wave sleep (SWS) quantity (SWS duration) and quality (slow wave activity, SWA) is one of these physiological factors. To test these hypotheses, we will perform community outreach in barbershops, churches and senior centers in Brooklyn and other NYC boroughs with which we have created substantial ties in recent years. In consultation with community stakeholders, we will recruit 150 cognitively normal AA elderly (age 60-75) and 60 age, sex, BMI, income and education matched non-Hispanic whites from the same geographical areas. We will first perform a medical and cognitive evaluation (Visit 1). Participants will then undergo 2 nights of home sleep monitoring using an unattended device to exclude OSA, followed by 7 days of actigraphy with a sleep log to record sleep duration. Both devices will be returned by mail. Subjects with reported total sleep time (TST) between 5 and 10 hours and absence of moderate to severe OSA will be invited to perform a 2-night nocturnal polysomnography (NPSG) (Nights 1-2) and a PiB-PET MR scan (Visit 2).
Objectives	Objective 1: To test if African ancestry (%AF) is associated with short SWS duration and poor SWA in older AAs. Objective 2: To test the effect of race and its interaction with baseline short SWS duration/poor SWA on longitudinal amyloid deposition. Objective 3: To test the effect of race and baseline poor SWA on cognition. Secondary Objective 2.1: To test whether loss of sleep-dependent spatial navigational memory at baseline is a predictor of cognitive decline.
Methodology	30-36 month longitudinal study
Endpoint	Primary endpoint is longitudinal increase in amyloid deposition
Study Duration	5 years
Participant Duration	30-36 months

CONFIDENTIAL

[figure not shown]
This material is the property of the NYU School of Medicine and Langone Medical Center. Do not disclose or use except as authorized in writing by the study sponsor

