4.7 Participant Withdrawal or Termination

4.7.1 Reasons for Withdrawal or Termination

Participants are free to withdraw from participation in the study at any time upon request. An investigator may terminate participation in the study if:

- Any clinical adverse event (AE), laboratory abnormality, or other medical condition or situation occurs such that continued participation in the study would not be in the best interest of the participant.
- The participant meets an exclusion criterion (either newly developed or not previously recognized) that precludes further study participation during the 2-year follow-up.

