9.3 Statistical Methods

General considerations: we will incorporate standard techniques such as omnibus tests and appropriate adjustments to significance (α) levels (*e.g.*, Bonferroni correction) for *post-hoc* contrasts to control for multiple comparisons. Both selection and attrition biases might occur. Appropriate techniques (*e.g.*, Heckman 2-stage approach (GEE Probit Model)^{254;255} and Monte Carlo (EM algorithm)²⁵⁶ will be used to address biases or missing data. Attributes of those who withdrew to follow-up will be contrasted with completers to determine sources of attrition biases. Since only two time points will be analyzed, we will use linear regression models with the annual rate of amyloid change as dependent variable. Significance will be defined by $p < .05$ where p will be Bonferroni corrected when testing *post-hoc* contrasts.

- **Hypothesis (1)**: H1.1) for %AF associations, linear regression models, with each of SWS characteristics as the dependent variable, will be regressed on %AF controlling for age, sex, BMI, AHI, TST, sleep efficiency and WASO. H1.2) This model will test interaction by including the best SWS predictor as dependent variable, the psychosocial factor as a classification factor, %AF and the term created as the cross product of psychosocial factors and %AF.
- **Hypothesis 2-3 (H2-3)**: First we will calculate the associations between race and AD_{PiB}mask represented both as binary (AA *vs.* white) and numeric (%AF). Further analyses will use the representation (s) of race significantly associated with amyloid burden. Second, we will use hierarchical

CONFIDENTIAL

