linear regression, with rate of change of AD_{PiB}mask as the dependent variable and race as independent, adjusting for the matching factors: age, sex, BMI, education and annual income (block 1); ApoE4 and ABCA7 (block 2); DWML volumes, DKI indices and mPFC volume (block 3); and SWS characteristic (*e.g.* relative SWA) (block 4). Other covariates (*e.g.*, psychosocial) will be included in the final models if significantly different between AAs and whites as indicated by unequal variance t tests. Although we anticipate that relative SWA will be the best predictor of longitudinal change in AD_{PiB}mask, the best fitting model will be then replicated with each of the other SWS characteristics not listed before. On a final step, we will test whether the effect of SWS on amyloid deposition is different (*i.e.*, stronger) among AAs. The model would include AD_{PiB}mask change, the binary indicator of race (AA=1 *vs.* white=0) and SWA as described in H1.2. If the interaction is significant, it will imply that the effect of SWA on amyloid varies as a function of race. The sign of the estimated coefficient for this term would indicate whether SWA has a significantly stronger or weaker effect among AA. Exploratory Hypothesis: cognitive z-score change in subjects that show improvement in maze CT will be compared with those that don't show improvement using ANCOVA controlling for age, sex, BMI, race, education and ApoE4 status.

- **Post-hoc analyses**: a subset of *post-hoc* analyses will be performed by controlling by PiB levels at baseline and by splitting the sample into PiB+ and PiB- at baseline and performing a separate analysis for each subset. Stratified analyses will also be performed for men and women, as well as for AAs and whites. In addition, we will formally test the impact of PiB status (defined as PiB SUVR \geq 1.4) on the association of sleep measures with longitudinal increases in AD_{PiB}mask. Although we do not anticipate that sleep or SWS characteristics will change over the follow-up period, *post-hoc* analyses will be performed by assessing longitudinal changes in the sleep measures as correlates and predictors of longitudinal changes in the outcomes measures, using paired sample t-tests to assess the change in outcomes and sleep.

10 Source Documents and Access to Source Data/Documents

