13.3 Participant Reimbursements or Payments

Participants will receive \$150 per NPSG and \$200 for the PET-MR scan for a total of \$500 for the baseline evaluation and \$500 for the 24 fu visit. Subjects will be compensated with \$75 for the 12 month fu visit, totaling \$1,075 for entire study completion. Payments are incremental and not contingent upon completing the study.

14 Study Administration

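### Follow-up length is stated inconsistently across sections, and cognitive change, unlike amyloid change, has no stated adjustment for elapsed time

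*Combined protocol and SAP*

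**What the plan says.** The follow-up that supplies the longitudinal endpoints is described in several ways.

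- Protocol Summary, Methodology: "30-36 month longitudinal study". Participant Duration gives the same range.
- Section 4.5: "The study will be over the course of 30 months per participant", then "although we will provide flexible visit options and up to 35 months will be allowed".
- Section 4.4: retention is "expected 95% at the 2.5 year follow-up". Section 6.1 uses the same 2.5-year interval for the maze test.
- Section 5.2: the follow-up visits are labelled 30-month, with no window.
- Section 4.7.1: an investigator may end participation if an exclusion criterion "precludes further study participation during the 2-year follow-up".
- Section 13.3: a payment is set "for the 24 fu visit". The 12-month visit is listed separately, so the unit is presumably months.

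On analysis, section 9.3 states for amyloid that "we will use linear regression models with the annual rate of amyloid change as dependent variable". For the exploratory hypothesis, "cognitive z-score change in subjects that show improvement in maze CT will be compared" with that of non-improvers by ANCOVA. The covariates are race, age, sex, education, BMI and ApoE4, and there is no term for follow-up time. For the main Aim 3 hypotheses, the joint paragraph for Hypotheses 2 and 3 names only the rate of change of the PiB index as outcome. Section 9.1 speaks of longitudinal changes in cognition without a scale, and section 3.1 says Aim 3 will be handled much as Aim 2.

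**The concern.** Two gaps meet here. First, staff cannot tell which visits are on schedule. A scan and cognitive battery at month 36 fit the Protocol Summary but exceed the limit in section 4.5, and section 12.3 requires deviations to be reported within 5 working days. Second, flexible timing is a deliberate retention tool (sections 4.4 and 4.5), so intervals will vary. The plan allows for that in amyloid but does not say how it does so in cognition.

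If cognition changes steadily, a participant tested later shows more raw change at the same yearly rate. Should later testing be more common in one race, at one level of slow wave activity (SWA), or in one maze group, part of the cognitive contrast would be elapsed time. Section 9.3 compares people who withdrew with completers, but nothing in the plan compares the interval among completers. An analyst could also choose raw or annualised change for Aim 3 after seeing the data and claim to have followed the plan either way.

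**Working it through.** **Plan's own figure.** Section 9.2 claims 80% power for slow wave sleep measures that explain 3% of variance in longitudinal change after covariates explain 25%, with complete data from 200. For a one-degree-of-freedom R² increment:

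- f² = 0.03 / (1 − 0.25 − 0.03) = 0.0417
- noncentrality = 200 × 0.0417 = 8.33
- power at α = 0.05 is 0.819, whether 0 or 15 covariates are fitted

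This reproduces the stated 80% to within 2 points.

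**Spread of intervals.** 35/30 = 1.17 and 36/30 = 1.20. At a constant yearly slope, raw change differs by the same ratios.

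**Assumptions.** The documents give no cognitive slope and no SD of change. I assume a mean slope from 0 to −0.10 z per year and an SD of change from 0.3 to 0.5 z.

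**Extra apparent change from later testing** = slope × extra months / 12.

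- 5 months: 0 to −0.10 × 5/12 = −0.042 z
- 6 months: 0 to −0.10 × 6/12 = −0.050 z

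**Case A: interval unrelated to race, sleep or maze group.** Take a uniform spread over 30-36 months.

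- SD of time = (6/12)/√12 = 0.144 years
- Largest added variance = (0.10 × 0.144)² = 0.000208
- Largest share of outcome variance = 0.000208 / (0.3² + 0.000208) = 0.23%. Over 30-35 months it is 0.16%.
- Shrinking both the 3% and the 25% by that share gives power of 0.818, against 0.819

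The lowest power in any scenario run was 0.814. That required a spread of 24-36 months, which the schedule does not contain.

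**Case B: mean interval differs by race.** Split 200 in the planned 150:60 ratio, giving 143 and 57. With SD 0.3:

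- SE = 0.3 × √(1/143 + 1/57) = 0.047
- 3-month difference at −0.10 z per year: bias = −0.025 z, or 0.53 SE, so type I error is 8.3%
- The same difference with SD 0.5: 6.2%
- Slope −0.02 and SD 0.5: 5.05%
- Slope 0: exactly 5%

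The range for a 3-month difference is thus 5.0% to 8.3%. For a 6-month difference it is 5.0% to 18.6%, but that needs all of one group at month 30 and all of the other at month 36, so it is an extreme.

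Case B uses the race contrast because its group sizes are known. The maze-improvement groups in the exploratory ANCOVA have no planned sizes, but the mechanism is the same.

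**The case against.** **The operative text agrees on 30 months.** Sections 4.4, 4.5, 5.2 and 6.1 all say 30 months or 2.5 years, and Attachment A lists a baseline, a 12-month visit and one later follow-up. A reader might infer from sections 4.7.1 and 13.3 that the endpoint visit could fall at 24 months. The documents do not support that. One mention describes a period in a termination clause and the other is a payment line, and no 24-month assessment is scheduled. What stands is the conflict between 35 and 36 months, the missing window in 5.2, and two stray references that need correcting.

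**Aim 3 may already be meant as a rate.** The heading shared with Hypothesis 2 and the cross-reference in section 3.1 allow that reading. A reader might infer that all cognitive outcomes will be analysed as raw change, but the plan leaves the Aim 3 outcome undefined. Only the exploratory ANCOVA names a change score without a time term, and it does so by omission.

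**Unequal follow-up need not appear as decline.** A reader might infer that it must. That needs a non-zero mean slope in people enrolled as cognitively normal. Practice gains would reverse the sign. The z-scores use age-adjusted norms (section 6.1), and re-applying them at follow-up age, which is not stated, could remove expected ageing change. Bias further needs timing to differ between the groups compared. Both races share zip codes and one schedule, and nothing in the documents shows a difference. These points stand.

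**Dividing by time has a price.** With constant error per assessment, the error variance of a yearly rate at 30 months is (36/30)² = 1.44 times that at 36 months. This is true, and it is why an interval covariate is offered as an alternative.

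**Conclusion.** The inconsistency in follow-up time is real and lies in current text. It should be reconciled, because it decides which endpoint visits count as on schedule. The analysis gap is also real but limited: the exploratory ANCOVA lacks any adjustment for elapsed time, and the Aim 3 cognitive and maze outcomes have no stated time scale. The primary amyloid endpoint is already annualised and is not affected by that gap.

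The likely effect is small. With timing unrelated to the groups, the cost is about 0.2% of outcome variance and a negligible loss of power. A bias that matters needs both a non-zero mean slope and a group difference in interval. With a 3-month difference by race, type I error could reach 8.3% at the steepest slope and smallest SD considered. All these sizes rest on assumed slopes and SDs. The case for acting is that the plan has no means of detecting a group difference in interval, and that the remedy costs almost nothing.

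**What to change.** 1. Reconcile the Protocol Summary and sections 4.5, 4.7.1, 5.2 and 13.3 to one follow-up time and one window. Which time and window is for the sponsor to decide.
2. In section 9.3, name the dependent variables for H3.1 and H3.2, including the maze. State that these changes and the exploratory cognitive change are analysed per year of actual elapsed time, as for amyloid, or with the exact interval as a covariate. Choose one before the data are examined.
3. Tabulate the interval by race.

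The cost is wording in the five places listed and in 9.3, plus either one derived variable or one degree of freedom. No new data are needed, since annualising amyloid already requires elapsed time. The stated power of 80% is unaffected.

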4.6 Total Number of Participants and Sites

Up to 270 people will be enrolled to reach a goal of 210 evaluable participants (accounting for attrition).

CONFIDENTIAL

4.7 Participant Withdrawal or Termination

4.7.1 Reasons for Withdrawal or Termination

Participants are free to withdraw from participation in the study at any time upon request. An investigator may terminate participation in the study if:

- Any clinical adverse event (AE), laboratory abnormality, or other medical condition or situation occurs such that continued participation in the study would not be in the best interest of the participant.
- The participant meets an exclusion criterion (either newly developed or not previously recognized) that precludes further study participation during the 2-year follow-up.

4.7.2 Handling of Participant Withdrawals or Termination

For a variety of reasons, subjects may decide to withdraw from the study, or the PI may decide to terminate a subject's participation regardless of whether the subject wishes to continue participating. Data collected on the subject to the point of withdrawal will remain part of the study database and will not be removed. The consent document will give the subject the option of having his/her data anonymized. In all cases we will ask subjects who are withdrawing whether they wish to provide continued clinical follow-up subsequent to their withdrawal (*i.e.* yearly clinical interview by [name] and neuropsychological evaluations that are part of the UDS-3). Under this circumstance, the discussion with the subject will distinguish between study-related evaluations and continued follow-up of associated clinical outcome information, such as medical course obtained through a clinical interview and neuropsychological tests. A second option will be to continue participation through the ADC cohort. In all cases we will address the maintenance of privacy and confidentiality of the subject's information.

If a subject: *i*) withdraws from the study, *ii*) does not consent to continued follow-up of associated clinical outcome information, and *iii*) does not request removal of their data, the PI will not access for purposes related to the study the subject's medical record or other confidential records requiring the subject's consent. However, the PI may review study data related to the subject collected prior to the subject's withdrawal from the study, and may consult public records, such as those establishing survival status. A subject will be considered lost to follow-up after non-response to: 5-10 phone calls to the telephone number provided by the subject, 5 phone calls to the study partner, 3 emails and 1 certified letter to the participant home address. Replacement will be allowed in those subjects that withdraw from the study in less than 12 months after the baseline visit.

4.7.3 Premature Termination or Suspension of Study

This study may be temporarily suspended or prematurely terminated if there is sufficient reasonable cause. Written notification, documenting the reason for study suspension or termination, will be provided by the suspending or terminating party to the investigator, funding agency, and regulatory authorities. If the study is prematurely terminated or suspended, the PI will promptly inform the IRB and will provide the reason(s) for the termination or suspension.

Circumstances that may warrant termination or suspension include, but are not limited to:

- Determination of unexpected, significant, or unacceptable risk to participants
- Insufficient compliance to protocol requirements
- Data that are not sufficiently complete and/or evaluable

Study may resume once concerns about safety, protocol compliance, data quality are addressed and satisfy the sponsor and/or IRB.

CONFIDENTIAL

5 Study Schedule

5.1 Screening

Screening Visit (Day 0)

- Obtain verbal consent from potential participants.
- Fill out the following forms: Center for Epidemiologic Studies Depression Scale (CES-D), Medical Outcomes Study Short Form (MOSSF), ARES-TM Questionnaire
- Review medical history to determine eligibility based on inclusion/exclusion criteria.
- Review medications history to determine eligibility based on inclusion/exclusion criteria.
- Schedule study visits for individuals who are eligible and available for the duration of the study.
- Provide potential participants with instructions needed to prepare for first study visit

5.2 Enrollment/Baseline

Enrollment/Baseline Visit 1 (Visit 1, Day 1)

This visit will occur at the Center for Brain Health (CBH) [name]

- Obtain and document consent from participant on study informed consent form (ICF).
- Obtain demographic information, medical history, medication history, alcohol and tobacco use history.
- Clinical evaluation and record results of physical examinations
- Collect blood and urine for clinical labs and in order to obtain ApoE genotyping
- Perform EKG
- Administration of the clinical section of the UDS 3.0 cognitive evaluation
- Administration of the WHICAP cognitive battery
- Verify inclusion/exclusion criteria after clinical interview, clinical labs and neuropsychological tests.
- Participants will receive a one week sleep diary, WatchPAT to wear for 1 night and an actigraph to wear during the remaining 7 days of the week.

Baseline Visit 3 (Visit 2, Night 1/Day 2)

This visit will occur at the Mount Sinai Integrative Sleep Center (MSISC) [name]

- Nocturnal Polysomnography at their usual bedtime
- Provide actigraphy device to monitor naps and compliance with the instruction to not sleep between visits while at home.
- Provide breakfast.
- Subjects can go home for the day.

Baseline Visit 4 (Visit 3, Night 2/Day 3)

This visit will occur at the Mount Sinai Integrative Sleep Center (MSISC) [name]

- Virtual maze spatial navigational memory test training session.
- Nocturnal Polysomnography.
- Virtual maze spatial navigational memory test testing session.
- Provide breakfast

Baseline Visit 5 (Visit 4, Day 4)

- *This visit will occur at the Center for Brain Health and the Center for Biomedical Imaging ([name]) Complete UDS 3.0 Cognitive evaluation and sleep interview at the Center for Brain Health*

CONFIDENTIAL

This material is the property of the NYU School of Medicine and Langone Medical Center. Do not disclose or use except as authorized in writing by the study sponsor

- PiB PET-MR Scan: PiB PET-MR scan of your brain at the Center for Biomedical Imaging (Pregnancy urine test will be done on women prior to the exam)
 - PET/MR scans combine two types of imaging methods: Positron Emissions Tomography (PET) and Magnetic Resonance Imaging (MRI). PET uses radioactive tracers to produce images that can inform us how a particular compound is used by tissue or for identifying unique cell-types, such as Tau, in this study. MRI uses magnetic fields and radio waves to produce images that can inform us about structures and function of tissue in the body. Combining both techniques provides more useful information while reducing the amount of radiation exposure compared to a standard PET scan or PET/CT. A small amount of tracer known as ¹¹C-Pittsburgh compound-B (PiB) will be injected into a vein in your arm before the scan begins and a 60-min PET-MR scan will be performed 35 min after injection.

Followup Study Visit

12-Month Follow-Up Visit 1-day visit

This visit will occur at the Alzheimer's disease Center (ADC) [name]

- UDS 3.0 cognitive evaluation will be re-administered by Alzheimer's Disease Center clinicians and testers
- You will have a physical, neurological, and psychiatric examination along with collection of vital signs (heart rate, blood pressure, temperature, and breathing rate) and medical history including medications you take and surgeries you have had.
- Electrocardiogram (EKG): Assesses the electrical activity of your heart. Electrodes (sensors connected to wires on the EKG machine) will be attached to your chest, upper arms, and legs. The heart tracing will take approximately 10 minutes to complete.
- You will have a urinalysis for routine testing to screen for urinary infections. Blood will be drawn for clinical labs and to obtain DNA for ApoE genotyping (Baseline Visit 1 only). The total amount of blood to be donated for the baseline and follow-up visits up the study is equivalent to approximately 6 tablespoons of blood. No MRIs or additional procedures will be performed in the 12 month fu visit

30-month Follow-Up Visit 1 (Visit 1, Day 1)

This visit will occur at the Center for Brain Health (CBH) [name]

- Obtain demographic information, medical history, medication history, alcohol and tobacco use history
- Clinical evaluation and record results of physical examinations
- Collect blood for clinical labs
- Perform EKG
- Administration of the clinical section of the UDS 3.0 cognitive evaluation
- Administration of the WHICAP cognitive battery
- Verify inclusion/exclusion criteria after clinical interview, clinical labs and neuropsychological tests
- Participants will receive a one week sleep diary, and an actigraph to wear during the week.

30-month Follow-Up Visit 2 (Visit 2, Night 1)

This visit will occur at the Mount Sinai Integrative Sleep Center (MSISC) [name]

- Nocturnal Polysomnography at their usual bedtime
- Provide actigraphy device to monitor naps and compliance with the instruction to not sleep between visits while at home.
- Provide breakfast.
- Subjects can go home for the day.

30-month Follow-Up Visit 3 (Visit 3, Night 2/Day 3)

This visit will occur at the Mount Sinai Integrative Sleep Center (MSISC) [name]

- Virtual maze spatial navigational memory test training session.
- Nocturnal Polysomnography.
- Virtual maze spatial navigational memory test testing session.

CONFIDENTIAL

This material is the property of the NYU School of Medicine and Langone Medical Center. Do not disclose or use except as authorized in writing by the study sponsor

- Provide breakfast.

30-month Follow-Up Visit 4 (Visit 4/ Day 4) This visit will occur at the Center for Brain Health and the Center for Biomedical Imaging ([name]) Complete UDS 3.0 Cognitive evaluation and sleep interview at the Center for Brain Health

- Complete UDS 3.0 Cognitive evaluation
- PiB PET-MR Scan

